	
variables. The Wilcoxon rank-sum test, Chi-square test or Fisher exact test will be applied for comparing continuous or categorical variables between two arms, as appropriate. The proportion (and 95% confidence intervals) of patients with an increased temperature by at least 1°C at 8 hours from arrival to the trauma bay will be calculated and compared between two arms using Chi-square or Fisher exact test as appropriate. Linear mixed model will be used to search for significant time trends in two arms on the hourly body temperature measurements within the first eight hours of blanket application. To compare coagulation and perfusion parameters measured on arrival and over the first 8 hours, between two arms, linear mixed model will also be performed for the repeated measurements. P-value < 0.05 will be considered statistically significant.

--	---

[figure not shown]

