5.2.2 Exclusion Criteria

1. Transferred from another healthcare facility
2. Death in the trauma bay prior to randomization
3. Arrival to trauma bay with ongoing CPR
4. Patients with penetrating head injury with Glasgow Coma Scale of 3 AND loss of brain matter through the wound

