Patients will be randomized upon activation of the MHP according to a computer-generated allocation sequence using RedCap. If the patient is randomized to receive the intervention, the study research coordinator/assistant will activate the two Ready-Heat® blankets by opening the seal on the packaging. A trauma team member will place the blankets on the patient. As this is an open-label trial, only the statistician will remain blinded during the final analysis. Enrollment will occur 08:00-20:00hrs on weekdays with the aim of assessing feasibility of using the blanket when study coordinators are not always available to reinforce temperature monitoring, proper blanket placement, and compliance with keeping the blanket on the patient over the intervention period.

Data will be collected by the research assistants and medical students as the patients are enrolled in the trial during weekdays 8 am to 8 pm. REDCap will be used to register the collected variables.

Research Ethics Board (REB) approval of the protocol and the informed consent form will be obtained. A recruitment log of eligible and ineligible patients as well as reasons for non-consent will be kept. We anticipate that this study will take 24 months to complete.

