5.3.5.4 Return and Destruction of Investigational Product

Trauma Team members will be made aware of their responsibility to return any unused investigational products in the event the resuscitation is ended before applying the product (i.e.: patient death, termination of resuscitation). As per manufacturer's Instructions for Use (IFU) document, the Ready-Heat® blanket may be disposed of with regular waste as there are no harmful ingredients.

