5.4.1 Study Visits

The following information will be collected during study visits either in person or remotely reviewing electronic health records. During weekdays, 8 am to 8 pm, the research assistant will be following the patient across the different phases/locations of care and will be collecting data at the same time. Research assistants will access all documented data on the next weekday. Visits and specific data collection are detailed as follows:

5.4.1.1 Visit 1

On admission to the trauma bay: Demographics, injury characteristics and surgical management:

1. Date of injury
2. Time of injury
3. Sex
4. Age
5. Types of surgical procedures performed in the first 8 hours following hospital arrival
6. Date of arrival
7. Time of arrival
8. Time of randomization
9. Name of attending TTL and sub-TTL (if applicable)
10. Initial temperature recorded
11. Was the blanket placed on the patient? Yes/No
12. Time that the blanket was placed on the patient, if registered
13. Reason why blanket was not applied
14. Blanket applied directly to the patient's skin? Yes/No
15. Use of fluid warmers
16. Use of FAWB

5.4.1.2 Visit 2

Within the first eight hours of blanket application:

1. Location of the patient
2. Is the blanket kept on the patient? (Yes/No)
3. If not, what was the reason it was removed?
4. Temperature recorded, hourly (Yes/No)
5. If yes, the temperature recorded
6. Type of temperature measurement
7. Blanket applied directly to patient's skin? Yes/No
8. Use of FAWB
9. Use of fluid warmers

At discretion of the clinician, within the first eight hours of blanket application:

10. Coagulation (platelet count, INR, fibrinogen)
11. Perfusion parameters (pH, base deficit, serum lactate)
12. Hemoglobin

13. Number of units of red blood cells, plasma, platelets, and fibrinogen concentrate administered within the first 8 hours

5.4.1.3 Visit 3

At 24 hours post blanket application:

1. Number of units of red blood cells, plasma, platelets, and fibrinogen concentrate administered within the first 24 hours
2. Type of injury (blunt/penetrating)
3. Injury Severity Score (ISS)
4. Frequency of safety events with skin

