7.2 Final Analysis Plan

Demographic and clinical characteristics will be summarized in total and by two arms using mean, SD, median (interquartiles) and range for continuous variables, and percentages for categorical variables. Wilcoxon rank-sum test, Chi-square test or Fisher exact test will be applied for comparing continuous or categorical variables between two arms, as appropriate. To investigate the primary objective on the feasibility of using the Ready-Heat® chemical heating blanket, the proportion (and 95% CIs) of patients with an increased body temperature by at least 1°C at 8 hours from arrival to the trauma bay will be calculated and compared between two arms using Chi-square or Fisher exact test as appropriate. Line graph (with mean and SD) of body temperature over the first 8 hours of blanket application will be plotted for two treatment arms. To search for significant time trends in two arms on the hourly body

temperature measurements within first 8 hours of blanket application, linear mixed effects repeated model will be performed with both fixed (time in hours, treatment arms, and arms by time interaction) and random (patient) effects. To compare treatment effects on the coagulation parameters (platelet count, INR, fibrinogen level), perfusion parameters (pH, base deficit, serum lactate), and hemoglobin levels measured on arrival and over the first 8 hours, linear mixed effects repeated model will also be performed with both fixed and random effects. Skewness and Kurtosis will be tested on the distribution of coagulation, perfusion and hemoglobin parameters. Natural logarithm transformation will be applied to normalize the distribution if necessary. Descriptive analysis will be summarized in total and by arms for safety measurements (i.e., number of units of blood products transfused, number of times blanket is placed directly on patient skin, and number of times patients developed redness and/or skin burns). All analyses will be conducted using Statistical Analysis Software (SAS version 9.4, Cary, NC) and R package (version 4.3.0). P-value < 0.05 will be considered statistically significant.

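### The hourly temperature graph and mixed model start at blanket application, so randomised patients with no blanket or no recorded blanket time have no hour 0; separately, primary outcome 1 is timed from two different events

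*Combined protocol and SAP*

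**What the plan says.** **The blanket clock.** Section 7.2 plans a "Line graph (with mean and SD) of body temperature over the first 8 hours of blanket application" for the two arms. For the hourly readings it then specifies the model: "temperature measurements within first 8 hours of blanket application, linear mixed effects repeated model will be performed", with arm, time and arm-by-time as fixed effects and patient as random effect. The Statistical Analysis row of the Protocol Summary says the same: the model is to "search for significant time trends in two arms on the hourly body temperature measurements within the first eight hours of blanket application". Visit 2 (Section 5.4.1.2) collects hourly temperatures in that window.

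**Application comes after allocation and may be missing.** Section 5.3.1 states: "Patients will be randomized upon activation of the MHP". The blankets are opened and placed after that. Visit 1 (Section 5.4.1.1) records "Time that the blanket was placed on the patient, if registered" and, as the next item, "Reason why blanket was not applied". Section 5.3.5.4 provides for resuscitation ending, including by death, before the product is applied. The corresponding exclusion in Section 5.2.2 is only "Death in the trauma bay prior to randomization", so a patient who dies after randomisation stays randomised. Section 5.6 expects noncompliance to come from patient condition and from unfamiliarity with the protocol.

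**Primary outcome 1.** The Study Outcomes row of the Protocol Summary counts the eight hours from blanket placement. The Planned Use and Statistical Analysis rows of the same summary, Section 5.1, criterion 1 in Section 6.1 and the responder analysis in Section 7.2 all count from arrival. Section 3.4 counts from admission. The objective in Section 3.1 refers to the first eight hours with the blanket on the patient.

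**The concern.** A randomised comparison is protected when the start of follow-up is fixed for everyone at or before allocation. Here the start is an event after allocation whose occurrence and recording may depend on how sick the patient is; the plan itself names patient condition as an expected reason for non-use. A patient without that event, or without its time, cannot be placed on the time axis and has no defined window for hourly readings. The analyst must then either omit the patient or choose a start time ad hoc, and the plan gives no rule.

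This is the trial's only longitudinal between-arm comparison of temperature, it is tested at P < 0.05, and the pilot is meant to inform a definitive trial. The second point is simpler: a primary outcome has one timing in one row of the summary and another timing in the body of the protocol.

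**Working it through.** **1. Who lacks an hour 0?**
- Intervention patient, blanket never applied: no hour 0. Visit 1 provides for this case.
- Intervention patient, blanket applied but time not registered: no usable hour 0. Visit 1 provides for this case too.
- Control patient: under Section 5.1 the trauma team places warmed blankets, so an hour 0 normally exists. It is missing if no blanket is placed or the time is not registered. The form speaks only of the blanket and does not say which event counts in this arm.
- Section 9.1 names a per-protocol set of patients with one or more blankets applied. It is not tied to the model and does not deal with an applied but untimed blanket.
- Arrival and randomisation times are both Visit 1 items without such a qualifier.

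**2. How many could be affected?** The plan's arm size reproduces: 29 / (1 − 0.20) = 36.25, rounded up to 37. Criterion 2 in Section 6.1 fails the study if the blanket is not applied and maintained in more than 20% of the intervention arm. Since 7/37 = 18.9% and 8/37 = 21.6%, at most 7 never-applied intervention patients are compatible with passing. That is an upper bound, because criterion 2 also counts blankets applied but not maintained. It does not limit untimed blankets or control patients.

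**3. What would omission do to an hourly mean?** Let p be the fraction of an arm omitted and d the mean temperature of kept patients minus that of omitted patients at that hour. Then

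mean(kept) − mean(all) = p × d.

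The documents give neither quantity. Assuming d = 0.5 to 2°C:

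| Omitted | p | d = 0.5°C | d = 1°C | d = 2°C |
|---|---|---|---|---|
| 1 of 37 | 0.027 | 0.014 | 0.027 | 0.054 |
| 7 of 37 | 0.189 | 0.095 | 0.189 | 0.378 |

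The between-arm difference moves by the difference between the two arms' p × d, so equal losses with equal d cancel. The figures concern patients still being measured; those who die before application have few readings on any clock.

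**4. What would it do to the trend?** If d is the same at every hour, all hourly means in the arm shift equally and the slope does not change. The arm-by-time term is biased only if the omitted patients' slopes differ from those of the others. The table therefore describes the line graph and differences in level, not the trend.

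**5. How far apart are the two timings of primary outcome 1?** They differ by the delay to application. Section 2.1.3 gives a median of 23 minutes in the earlier pilot, without stating the start point; assume arrival. At a steady rise of 1°C over 8 h (assumed), 23/480 × 1°C = 0.048°C. With complete hourly readings counted from application at t minutes after arrival, the eighth reading falls t minutes after the 480-minute mark and the seventh falls 60 − t minutes before it. For any t below 30 the eighth is the nearer, so both definitions select the same reading. The clock shift alone is minor. For a patient without a blanket time, however, the summary's version is undefined.

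**The case against.** The best defence is that the blanket clock is deliberate. The objective in Section 3.1 frames the comparison over the first eight hours with the blanket on, and criterion 3 in Section 6.1 uses that window too. This stands: the blanket-clock analysis should be kept, and a fix that ignored criterion 3 would create a new conflict. It does not supply an hour 0 for patients who have none.

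Second, nothing in the plan says such patients are dropped. This also stands: omission is inferred from silence. Section 5.6 has reasons documented and deviations assessed during analysis where necessary, but that is not a rule for placing these patients on the time axis.

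Third, the number affected may be small. Enrolment is confined to weekdays 08:00 to 20:00, when assistants follow patients, and study staff open the packages. Controls normally receive blankets as well. Widespread missing times are not shown, although Section 5.3.1 says coordinators are not always available.

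A reader might go further and infer that the 80% feasibility decision is at risk. The documents do not support that. Criterion 1 and its planned analysis agree on the arrival clock, the proportion needs no blanket time, and no feasibility criterion depends on the mixed model. Nor can p × d be read as bias in the model's time trend, for the reason in step 4.

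**Conclusion.** The concern holds in limited form. The line graph, the hourly mixed model and the Visit 2 collection run on a clock that some randomised patients may not have, and the plan does not say how those patients are handled. If they are left out, the comparison is conditioned on a post-randomisation event that the protocol itself links in part to patient condition.

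The size is unknown. With d assumed at 0.5 to 2°C, an arm's hourly mean moves by 0.01 to 0.05°C for one patient omitted. For seven never-applied intervention patients, the most that criterion 2 tolerates, it moves by 0.09 to 0.38°C. This is a cheap improvement to a secondary analysis.

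The timing of primary outcome 1 is an explicit inconsistency and must be reconciled, although its numerical effect at a 23-minute delay is small.

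**What to change.** - **One origin.** For the 8 h responder outcome, the line graph and the mixed model, use a start that every randomised patient has and that is already collected: arrival, which is the clock of the 80% rule, or randomisation if it is used for all three.
- **Population.** State that all randomised patients are analysed by assigned arm, subject to the data-withdrawal right in Section 5.3.1.
- **Collection.** In Section 5.4.1.2, collect charted temperatures from arrival to the later of 8 h on the common clock and 8 h after application, including patients with no blanket. Both windows are then covered.
- **Blanket clock.** Keep the blanket-application graph and model as a supplementary exposure analysis, which preserves the Section 3.1 objective.
- **Criterion 3.** Leave it on the blanket clock, but use the common origin for enrolled patients without a blanket time so that they stay in the denominator.
- **Wording.** Reconcile primary outcome 1 in the Protocol Summary, and Sections 3.1 and 3.4, with the other summary rows and Sections 5.1, 6.1 and 7.2.

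The cost is wording changes, a little extra chart abstraction and one supplementary analysis. Section 5.4.1 already has research assistants going back to the documented data on the next weekday. The duration of blanket use is not touched.

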3.3 Secondary Feasibility Outcomes

2- Feasibility of applying and keeping the 2 blankets in the trauma bay
3- Feasibility of keeping the 2 blankets in the CT scanner suite
4- Feasibility of keeping the 2 blankets in the ED
5- Feasibility of keeping at least one of the blanket in the OR or IR suite (one can be removed for procedures and re-applied at the end of the intervention)
6- Feasibility of keeping the 2 blankets in PACU (for example one blanket is removed in the OR and reapplied at the end of the procedures and kept in PACU before the patient is transferred to the ICU)
7- Feasibility of keeping the 2 blankets in the ICU up to 8 hours of until patient achieves 37.5 degrees Celsius.
8- Reasons why the blanket was not maintained at each of the next phase of care (CT scanner suite, IR suite, OR, ED, ICU)

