3.5 Clinical Outcomes

10- Proportion of adherence to body temperature measurement throughout different phases of care (i.e.: ED, CT scanner suite, OR, IR suite, ICU)
11 -Use of concurrent warming strategies(i.e. fluid warmers, FAWB, etc.) within the first eight hours of blanket application in conjunction with, or replacement of, the Ready-Heat® chemical heating blanket

- 12- Number of units of blood products (red blood cells, plasma, platelets, and fibrinogen concentrate) transfused within 24 hours post arrival to the trauma bay
- 13- Coagulation (platelet count, INR, fibrinogen level) and perfusion parameters (pH, base deficit, serum lactate) measured on arrival, and at the next time points collected as per clinician discretion
- 14- Hemoglobin level measured on arrival, and at the next time points collected as per clinician discretion

3.6 Safety Outcomes:

- 15 - Number of times blanket is placed directly on the patient skin
- 16 - Number of times patients developed redness and/or skin burns

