5.0 STUDY METHODS

5.1 Study Design

This will be a pilot, feasibility, prospective, open-label (with blinded outcome assessors) RCT to evaluate the feasibility of using two Ready-Heat® half blankets to increase temperature by at least 1°C at eight hours from arrival to the trauma bay, in severely injured bleeding trauma patients where a MHP is activated. A total of 74 participants will be randomized in a 1:1 ratio, to receive the intervention - two Ready-Heat® 4-panel half blankets applied indirectly (as per manufacturer's directions) with two flannel blankets placed under them, or the control - two warmed blankets (current standard of care) only. The study will take place at Sunnybrook Health Sciences Centre (SHSC). The patient will be screened in the trauma bay and enrolled by the TTL. Upon confirming eligibility for the study, a study research coordinator/assistant will randomize using a web-based randomization sequence built into REDCap. If the patient is randomized to receive the intervention, two Ready-Heat® blankets will be activated by opening the seal on the packaging and affixed to the blood product cooler to be given to the trauma team in the trauma bay. As this is an open-label trial, only the statistician will remain blinded during the final analysis. Enrollment will occur during weekdays between 0800-2000hrs with the aim of assessing feasibility of using the blanket when study coordinators are not always available to reinforce temperature monitoring, proper blanket placement, and compliance with keeping the blanket on the patient over the intervention period. Subjects in the control arm will have two warmed blankets obtained from a blanket warmer appliance in the trauma bay and will be applied on the patient by the trauma team. Temporary removal of the blanket and partial exposure of the patient may be necessary to facilitate clinical procedures. In the intervention arm, two separate four-panel blankets will be used to allow for temporary exposure for clinical procedures while still maintaining coverage for the rest of the body (i.e., 1 four-panel blanket can be applied to the torso while a fractured femur is reduced). Clinicians will be educated to keep the intervention warmer on the patient until 8 hours from time of blanket application. If there is a need to remove the intervention prior to the completion of 8 hours, the clinical team will document the reason (e.g., adverse reaction, interference with procedure, etc.). In this case, clinical teams will be educated to transition to the current standard of care (warmed blankets or

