5.3.3.5 Intervention arm

If the patient is randomized to receive the intervention, the two Ready-Heat® blankets will be activated by opening the seal on the packaging and given to the trauma team in the trauma bay. As this is an open-label trial, only the statistician will remain blinded during the final analysis. Subjects in the control arm will have a warmed blanket obtained from a blanket warmer appliance in the trauma bay.

Temporary removal of the blanket and partial exposure of the patient may be necessary to facilitate clinical procedures. In the intervention arm, two separate Ready-Heat four-panel blankets will be used to allow for temporary exposure for clinical procedures while still maintaining coverage for the rest of the body. Clinicians will be educated to keep the interventional products until the 8 hours post blanket application are completed. If an interventional product becomes soiled before the prescribed 8 hour period, a replacement product may be dispensed by contacting the Blood Bank. If there is a need to remove the intervention prior to the completion of 8 hours, the clinical team will document the reason (e.g., adverse reaction, interference with procedure, etc.). In this case, clinical teams will be educated to transition to the current standard of care (warmed blankets, or FAWB). If at least one of the two blankets remained until 8 hours post, clinical teams will be instructed to remove them and apply the current standard of care.

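### The hourly temperature model names no random slope, residual covariance or degrees-of-freedom method; fitted with the listed terms only, its arm-by-time test is anti-conservative when patients warm at different rates

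*Combined protocol and SAP*

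**What the plan says.** Section 7.2 (Final Analysis Plan) states that for hourly body temperature over the first 8 hours of blanket application a "linear mixed effects repeated model will be performed", "with both fixed (time in hours, treatment arms, and arms by time interaction) and random (patient) effects". Significance is set at P<0.05. The section does not say whether time is continuous or categorical. It names no random slope, residual covariance structure or degrees-of-freedom method. The Statistical Analysis entry of the Protocol Summary adds none of these: "Linear mixed model will be used to search for significant time trends in two arms on the hourly body temperature measurements".

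Other sections give reasons to expect warming rates to differ between patients:

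- Section 5.1: "Temporary removal of the blanket and partial exposure of the patient may be necessary to facilitate clinical procedures".
- Section 5.3.3.5: "If there is a need to remove the intervention prior to the completion of 8 hours, the clinical team will document the reason". Those patients then move to standard care.
- Section 3.3 lists as an outcome "Reasons why the blanket was not maintained at each of the next phase of care".
- Section 3.5 records concurrent warming (fluid warmers, forced air) used with or instead of the study blanket.

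**The concern.** A random intercept lets patients start at different temperatures but makes everyone in an arm warm at the same rate. If rates really differ, the model treats that spread as hour-to-hour noise, averages it over all the readings, and reports too small a standard error for the difference in slopes. More patients do not cure this, because the true and the reported variance shrink together.

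The consequence is that a chance difference in slopes could be reported as a warming effect at P<0.05, with a confidence interval that is too narrow. Section 2.2 makes the effect on temperature an aim and says the findings will support a grant for a larger trial. Section 7.1 says the pilot should improve estimates of the numbers for a definitive trial. An overconfident slope difference would feed into both.

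**Working it through.** **The plan's own figure.** There is none for this model. Section 7.1 sizes the trial on the precision of an 80% compliance rate. Its tabulated confidence coefficient of 0.95529 at n = 57 reproduces as exact binomial coverage, but it involves no temperature variance.

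**Inputs from the documents.** Alpha 0.05 (taken as two-sided); 29 completers per arm (37 randomized); hourly readings over 8 hours. That is T = 9 time points if hour 0 is included (sum of squares of time Sxx = 60) or T = 8 if not (Sxx = 42).

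**Assumed inputs.** Residual SD σ = 0.3°C, varied to 0.2 and 0.5; SD of patient slopes τ = 0, 0.03, 0.05 and 0.10°C/h; no true arm effect.

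**Formulas (complete, balanced readings).** The arm-by-time estimate is the difference in mean patient slopes.

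- True variance of one patient's slope: τ² + σ²/Sxx.
- With R = τ²·Sxx/σ², the variance reported by the random-intercept model: (σ²/Sxx)·(1 + R/(T−1)). Only one of each patient's T−1 within-patient degrees of freedom carries the slope spread.
- Ratio of true to reported variance: (1 + R)/(1 + R/(T−1)).
- Type I error: 2·[1 − Φ(1.96/√ratio)].

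**Worked case, τ = 0.05, σ = 0.3.**

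- T = 9: true variance 0.0025 + 0.09/60 = 0.0040. R = 0.0025 × 60/0.09 = 1.667. Reported variance 0.0015 × (1 + 1.667/8) = 0.00181. Ratio 2.21; 1.96/1.486 = 1.319; type I error 18.7%.
- T = 8: true variance 0.0025 + 0.09/42 = 0.00464. R = 1.167. Reported variance 0.00214 × (1 + 1.167/7) = 0.0025. Ratio 1.86; type I error 15.0%.

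**Over the range, σ = 0.3°C.**

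| Slope SD (°C/h) | Ratio, T = 9 | Type I, T = 9 | Ratio, T = 8 | Type I, T = 8 |
|---|---|---|---|---|
| 0 | 1.00 | 5.0% | 1.00 | 5.0% |
| 0.03 | 1.49 | 10.8% | 1.34 | 9.0% |
| 0.05 | 2.21 | 18.7% | 1.86 | 15.0% |
| 0.10 | 4.18 | 33.8% | 3.40 | 28.8% |

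At slope SD 0.05, type I error is 9.0% (T = 8) to 10.8% (T = 9) with σ = 0.5°C, and 22.7% to 27.6% with σ = 0.2°C.

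**Simulation check (3,000 null runs per setting, REML, 29 per arm, σ = 0.3, assumed arrival SD 0.8°C).** For slope SD 0 / 0.03 / 0.05 / 0.10:

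- Nine complete readings: 5 / 10 / 18 / 33%.
- Eight time points: 5 / 10 / 15 / 30%.
- 20% of readings missing at random: 5 / 10 / 17 / 32%.

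At slope SD 0.05 with 20% missing, the rate is 16% with 37 per arm and 12% if both arms plateau after 4 hours. With 40% missing it is 13%.

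**Categorical time, same random intercept (10,000 runs, hours 0 to 8).** The overall interaction test gives 5.1 / 5.4 / 6.8 / 9.8%.

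**Check of the remedy (20% missing).** A random intercept plus slope with Kenward-Roger gives 3.8 / 4.9 / 5.1 / 5.9%. Switching to a t-test of per-patient slopes when the slope variance is estimated as zero or the fit fails gives 5.0 / 4.7 / 4.5 / 4.8%.

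**The case against.** The strongest reply is that the plan does not commit to the faulty model. The word *repeated* in Section 7.2 leaves room for a within-patient covariance, and categorical time would keep the test near nominal except at the largest slope SD. This stands: a reader might infer that the plan has chosen a random-intercept model with independent residuals, but the text does not say so. What remains is that the listed terms, taken literally, give that model, and that *time in hours* and *time trends* lean towards linear time.

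Second, every variance here is assumed. This also stands. With equal slopes there is no inflation, and with a noisier residual it is modest.

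Third, this is a pilot sized on compliance, and the wording about searching for time trends is exploratory. This stands and limits the weight of the point. It does not remove it, because the plan attaches P<0.05 to the result and intends to build on it.

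Fourth, linear time with a random slope is not the only sound choice. Blanket removals, and the 37.5°C end point for keeping the blankets on in Section 3.3, may make warming non-linear. This is fair, and the fix allows for categorical time.

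**Conclusion.** The point holds as an under-specification with a conditional consequence. If the listed terms alone are fitted with linear time and independent residuals, type I error of the arm-by-time test is about 9–11%, 15–19% and 29–34% at slope SD 0.03, 0.05 and 0.10°C/h. This assumes residual SD 0.3°C and eight or nine complete readings. At slope SD 0.05, a nominal 95% interval would then cover about 81–85% of the time. It is a minor to moderate point about the exploratory temperature analysis.

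Three stronger readings are not supported:

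- A reader might infer that the feasibility decision is at risk. The Section 6.1 thresholds are proportions and do not use this test.
- A reader might infer that arm-by-time is the only between-arm test of the hourly series. The same model also lists an arm effect.
- A reader might infer that arrival temperature ("Initial temperature recorded", Section 5.4.1) ought to be a covariate for the 8-hour comparison. That comparison is the proportion with a rise of at least 1°C, so arrival temperature is already subtracted. On the assumptions above (29 per arm, slope SD 0.05, slopes unrelated to arrival temperature), the mean rise has SE √[2 × (64 × 0.0025 + 2 × 0.09)/29] = 0.153°C. Adjusting 8-hour temperature for arrival gives 0.146 to 0.151°C for arrival SD 0.4 to 1.0°C, a gain of about 1–5%. Larger apparent gains come only from comparing with an 8-hour difference implied by the model's fixed effects, which the plan never says it will report.

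**What to change.** In Section 7.2, before the data are seen:

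1. State how time is coded. If linear in hours, add a random slope for time per patient to the random intercept. If categorical, name an unstructured or other suitable within-patient covariance.
2. Name Kenward-Roger degrees of freedom.
3. Name a fallback for linear time: a two-sample t-test of per-patient least-squares slopes, for patients with at least two readings, if the model does not converge. State whether it also applies when the slope variance is estimated as zero.
4. Say whether the series includes an hour-0 reading and which reading that is. The series runs from blanket application, while the initial temperature is listed under admission.

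The cost is SAP wording and one model statement; no new measurement is needed for the random slope. The interval for the slope difference becomes wider. With 20% of readings missing, its SE is about 4% larger if slopes do not differ, and 18%, 39% and 85% larger at slope SD 0.03, 0.05 and 0.10°C/h. If slopes truly do not differ, about 54% of fits return a zero slope variance (0–6% otherwise), which is why the rule in item 3 should be fixed in advance.
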